## 1. Administrative Information

a. **Title:** Removing Surrogates Uncertainty to Reduce Fear and Anxiety after Cardiac Events (RESURFACE): A Randomized Pilot Intervention Study

a. **Public Title:** RESURFACE

b. **Registration Data:**

a. **Identifying Number:** IRB Number AAAR8497

b. **Primary Sponsor:** NIH/NIA

c. **Contact for Inquiries:**

[name], Principal Investigator

Associate Professor of Neurology (Neurocritical Care)

Dept of Neurology

[name]

[name]

[name]

[contact]

Email: [[contact]](mailto:[contact])

d. **Sites of Recruitment:** Columbia University Medical Center

e. **Health Condition(s) or Problem(s) Studied:** Psychological distress and poor sleep in surrogates of cardiac arrest (CA)

f. **Key Inclusion and Exclusion Criteria:**

*Inclusion Criteria:*

- 18 years of age or older
- Surrogate of an adult CA patient
- English- or Spanish-speaking
- Has a working smartphone, tablet, laptop, or other device with internet access

*Exclusion Criteria:*

- Any medical and/or psychiatric impairment precluding them from complying with the protocol
- Non-English and non-Spanish speaking
- Lack of internet/device access

- Surrogate of an adult CA patient who passed away
- Cannot be reached for initial contact (3 unsuccessful attempts made in ICU)
- Moved to the floor before initial contact can be established

g. **Study Type:** Unblinded two-arm pilot RCT of study intervention consisting of three online packages delivered in the ICU, inpatient floor, and at home for the intervention arm and care as usual for the control arm.

h. **Date of First Enrollment:** Pending

i. **Target Sample Size:** Up to 100 participants (recruiting 2:1 until at least 30 intervention arm participants conclude participation)

j. **Recruitment Status:** Not yet recruiting

c. **Roles and Responsibilities:**

**[name], MPH** [[contact]](mailto:[contact])

Principal Investigator, Associate Professor of Neurology (Neurocritical Care) and Director of the NeuroCardiac Comprehensive Care Clinical & Research Program.

## 2. Introduction

### a. Study Purpose and Rationale

The goal of this study is to test the feasibility and acceptability of Heartsight, an informational intervention, to reduce family members' uncertainty prevalent throughout the illness trajectory of their loved ones admitted with cardiac arrest (CA). CA is sudden and unexpected and carries substantial prognostic uncertainty during the early period of illness. Whereas patients are not conscious and often have little to no memory of the CA and the intensive care unit (ICU), immediate family members, who often act as *surrogates*, bear the burden of uncertainty from the moment they witness the CA at home or participate in resuscitation, make life-and-death decisions during hospitalization, and/or go home with their loved ones with new physical, cognitive, and emotional needs. Not surprisingly, many fear recurrence. The prevalence of clinically significant levels of posttraumatic stress (PTSS) is higher for surrogates (35%-50%) than for CA patients (30%) at discharge. Nearly one in two surrogates reports persistent PTSS at 1 year.

During an NIH-funded workshop eliciting “on-the-ground” perspectives about the experiences and needs of surrogates of patients with CA, key cross-cutting themes emerged, including (1) the challenges of uncertainty and the desire for information about illness and prognosis for recovery, (2) gaps in the provision of logistical information and support, (3) the importance of communicating compassion, sharing uncertainty, and responding to emotional and physical needs, and (4) a desire among surrogates to participate in the discussion and development of practices to improve support for future families in similar situations. These findings have been confirmed by 44 other studies recently summarized in our scoping review on the experiences of 3,598 surrogates of patients of CA patients across 15 countries and 5 continents. We found similar guidance in our needs prioritization exercise among a national sample of 575 surrogates of CA patients. In preparation for this study, we conducted a feasibility observational pilot with a mixed-methods approach where surrogates enrolled in the ICU completed serial qualitative interviews and quantitative assessments during the ICU and 1 month after discharge. The feasibility of recruiting family members of CA patients in an intervention study has further been demonstrated via Roybal Pilot- FAID Fear (PI [name]).

Uncertainty is not equivalent to mere ignorance; rather, a subjective experience of ignorance is a promising target mechanism that may underlie the success of informational interventions for improving the surrogate's cardiac anxiety, PTSS, and sleep. Illness uncertainty contributes to greater psychological distress and poor quality of life outcomes in chronic illnesses, e.g., chronic liver, lung, and heart disease, cancer, and more recently, after COVID-19. Appraisal theories of emotion have specified a direct relationship between uncertainty and emotions. **Uncertainty is also modifiable.** Informational programs may limit uncertainty and improve psychological profiles in cancer survivorship. Despite the surrogate's clear desire for information and high

levels of uncertainty after CA, information-based interventions have never been tested in an acute care setting.

## b. Objectives

We will test the feasibility and acceptability of Heartsight, an online informational intervention program developed by a multidisciplinary team of researchers and patient-surrogate stakeholders. It is a repository of bite-sized, simplified, information packages to be delivered at specific time points in the illness course: an **Understanding Cardiac Arrest** package in the ICU, a **Preparing for Discharge** package on the floor, and a **Focusing on You** package providing information on self-care and self-efficacy at 1 month post-discharge. Serial measurements of illness uncertainty and psychological distress (PTSS keyed to the cardiac event) will be performed at enrollment, discharge, and 3 months after discharge. We will objectively assess sleep duration via actigraphy for 1 week after hospital discharge.

**Aim 1:** Enroll up to 100 surrogates of CA patients to (**Aim 1a**) pilot recruitment and randomization (2:1) procedures, (**Aim 1b**) estimate retention rate at 3 months, and (**Aim 1c**) assess the engagement and utilization metrics through the website for frequency of access and time spent on each module of the packages.

**Exploratory Aim 1a:** Preliminary estimate of the association of intervention with the surrogate's uncertainty levels at 3 months post-discharge.

**Exploratory Aim 1b:** Preliminary estimate of the association of intervention with the surrogate's cardiac anxiety and posttraumatic stress at 3 months post-discharge.

**Exploratory Aim 1c:** Explore the lagged associations of uncertainty with cardiac anxiety and PTSS.

**Exploratory Aim 2:** Estimate the association of intervention with surrogates' sleep duration within the first week after hospital discharge.

[figure not shown]
## c. Study Design

This study is a two-arm unblinded RCT in which up to 100 adult CA surrogates will be enrolled over a 1-year period and randomized (using a 2:1 allocation until at least 30 intervention arm participants have completed their study participation) to either receive the Heartsight intervention or no additional information beyond usual treatment (control group). Data collection will occur at the initial approach in the ICU, on the floor, and at 3 months post-discharge. All participants will be English- and/or Spanish-speaking. If a CA patient dies at any point in the protocol, their surrogate is no longer eligible to continue in the study.

## 3. Methods

## a. RESURFACE Study Overview

### i. Study Flow

### ii. Study Setting

This study will take place at Columbia University Irving Medical Center (CUIMC). The study will have the option of remote phone or email visits following initial enrollment.

### iii. Sample Size

We plan to enroll up to 100 adult surrogates of CA patients in this study. All participants will be English and/or Spanish speakers. Participants will be enrolled and randomized (using a 2:1 allocation) to either the active informational intervention or the care as usual control group. Enrollment will end once 30 participants in the intervention arm have completed their participation in the study.

### iv. Eligibility Criteria

#### *Inclusion Criteria:*

- 18 years of age or older
- Surrogate of an adult CA patient
- English- or Spanish-speaking
- Has a working smartphone, tablet, laptop, or other device with internet access

#### *Exclusion Criteria:*

- Any medical and/or psychiatric impairment precluding them from complying with the protocol
- Non-English and non-Spanish speaking
- Lack of internet/device access
- Surrogate of an adult CA patient who passed away
- Cannot be reached for initial contact (3 unsuccessful attempts made in ICU)
- Moved to the floor before initial contact can be established

**v. Recruitment and Screening Procedures**

Our recruitment strategy will include recruiting adult surrogates of CUMC patients who experienced cardiac arrest (CA) and are currently in the ICU. The study team will first confirm eligibility by reviewing the electronic medical record, then approach surrogates after admission in the ICU, if the patient is still living. An electronic screening log will be maintained by study coordinators in the [CANOE-F spreadsheet under “ALL Eligibility RESURFACE.”](#)

The study coordinator will pitch RESURFACE to the surrogate using [this script](#).

Surrogates who are interested will complete the informed consent process with a study coordinator. The informed consent process includes explaining risks and benefits of the study, payment structure, voluntary nature of participation, procedures for termination, strategies for maintaining confidentiality, and contact information for the study. If surrogates are ready to consent now, they will provide their written consent by signing the consent form. Participants will also indicate to the study coordinator their preferred form of payment at this time (TruCentive e-gift card). Completed consent forms will be filed in the NeuroCardiac Care office, and a paper copy will be provided to participants.

If not interested in RESURFACE, surrogates will have the option to refer study coordinators to another family member who may be more interested in participating, and/or to participate in the CANOE-F parent study instead, which only requires one survey. Surrogates may also ask study coordinators to reapproach later if they would like more time to consider RESURFACE.

After 3 unsuccessful attempts to reach an eligible participant in the ICU for recruitment, they will be marked ineligible for participation in this study.

**vi. Participant Retention**

Every effort will be made by the PI and study team to ensure eligible participants complete each study visit and survey. We will use the following strategies to minimize loss to follow-up:

- Enhancing participant’s understanding of the study’s objectives and the protocol by reminding the participant of the study aim during study visits and leaving time for participants to ask questions about the study, if needed
- Building participant relations and participant satisfaction, with the study coordinator taking a central role on this effort (e.g., the study coordinator checking how family members are doing when approaching at baseline)

- Identifying low-use or no-use intervention arm participants at discharge and 3 months post-discharge and eliciting targeted user feedback via surveys
- Providing technical support, if requested, for intervention arm participants who are struggling to use Heartsight

If a participant does not return for study visits, study coordinators will make several contacts using all the contact information provided by the participant. This may include phone calls, emails, and/or asking the cardiac arrest survivor when their surrogate might next visit the hospital.

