**Between Visits 1 and 2:**

***Heartsight Intervention Package 1 (Understanding Cardiac Arrest):***

After completion of the baseline survey, participants assigned to the intervention arm will be emailed login and access details for their Heartsight account. These participants will be instructed to view the Understanding Cardiac Arrest package of articles, which provides information about cardiac arrest and the ICU, and provide article-specific feedback by leaving comments on the website. Participant utilization of Heartsight will be tracked using User Insights. Intervention arm participants who do not access Heartsight within 4 days of receiving access details will be sent a reminder email.

Participants assigned to the control arm will not receive any materials.

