### **Visit 2 (Discharge):**

#### ***Survey 2 (Discharge, 15 min):***

Study coordinators will monitor the electronic medical record to determine when participants will be discharged from the hospital. Approximately one day before discharge, study coordinators will approach participants to deliver the second survey. This survey, taken by participants in both arms, can be completed asynchronously in-person (on paper) or via REDCap (online). The discharge survey will contain questions about subjective perception of uncertainty (3 questions), illness uncertainty (Mishel Uncertainty in Illness Scale for Family Members, 31 questions), PTSS (PCL-5, 20 questions), cardiac anxiety (Cardiac Anxiety Questionnaire fear subscale, 8 questions), and social support (Enriched Social Support Instrument, 6 questions). Intervention arm participants who have been identified as viewing less than 25% of the Preparing for Discharge articles will receive two additional questions asking for user feedback.

Upon completion of the discharge survey, study coordinators will process the first \$50 payment to the participant. At this time, study coordinators will also provide all participants with a GENEActiv device, study log, stamped envelope for return, and instructions for proper use and return in 1 week.

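### The retention plan allows the study aim to be restated around the self-report outcome surveys of an unblinded trial, with no limit on wording or timing (minor)

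*Combined protocol and SAP*

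**What the plan says.** Section 3.a.vi (Participant Retention) gives "reminding the participant of the study aim during study visits" as one way of improving participants' understanding of the study, along with time for questions. The item is not restricted by arm. It does not say which aim is meant, how it should be put, or whether it comes before or after the survey.

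The surrounding design is as follows.

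- **Blinding.** Section 2.c: "This study is a two-arm unblinded RCT".
- **Comparator.** Section 3.a.ix, under each of the three Heartsight packages: "Participants assigned to the control arm will not receive any materials".
- **Direction.** The title begins "Removing Surrogates Uncertainty to Reduce Fear and Anxiety after Cardiac Events". Section 2.a describes Heartsight as an intervention "to reduce family members' uncertainty prevalent throughout the illness trajectory".
- **Visit 2.** Section 3.a.ix: "Approximately one day before discharge, study coordinators will approach participants to deliver the second survey". This survey holds the Mishel uncertainty scale, the PCL-5 and the fear subscale of the Cardiac Anxiety Questionnaire.
- **Visit 3.** The same three instruments are repeated, through REDCap or by telephone. Section 3.a.x has the coordinator check the participant's arm beforehand to pick the right survey version. On a call, the coordinator may enter the answers directly.
- **Analysis.** Section 3.b.iii plans 95% bootstrap confidence intervals for the between-arm mean differences in uncertainty (Exploratory Aim 1a) and in cardiac anxiety and PCL-5 (Exploratory Aim 1b).

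**The concern.** Knowledge of allocation cannot be avoided in this trial. Participants either hold a Heartsight login or have received nothing, and no attention control evens this out. Prompting the hypothesis at the time of measurement is a separate matter, and it can be avoided. A Heartsight user who has just heard that the programme is meant to lower uncertainty may lean towards lower scores on the uncertainty scale. A control who hears the same thing has no reason to lean that way, and may lean the other way. Such a difference in reporting would enter the mean differences of Exploratory Aims 1a and 1b as if it were an effect of the intervention, and a larger sample would not remove it.

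**Working it through.** **Reading the sections together**

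1. *Are the visits the measurement contacts?* Yes. Section 3.a.ix defines three visits, and each consists of a survey. Exploratory Aims 1a and 1b are defined at 3 months (section 2.b), so Visit 3 matters most for the mean differences.
2. *Are the outcomes self-reported?* Yes, for uncertainty, PTSS and cardiac anxiety. Sleep duration is measured by actigraphy.
3. *Could participants and staff know the arm?* Yes, at both visits. Baseline is less exposed: randomisation precedes the baseline survey, but Heartsight access is emailed only after it is completed.
4. *Does the visible text order or neutralise the reminder?* No. The Visit 2 and Visit 3 procedures in section 3.a.x do not mention it. They describe no neutral wording, no masked assessor and no rule that the survey comes first.
5. *Can reminder and measurement coincide?* Yes, most directly on a Visit 3 telephone survey. With a paper survey at Visit 2 there are two contacts, drop-off and pick-up, and the plan would permit the reminder at either.

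**Scale, for illustration only**

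The plan gives no figure for reporting bias and no SD for these scales. Its one precision figure concerns retention: 0.90 ± 1.96 × √(0.9 × 0.1/30) gives 79.3% to 100.7%, capped at 100%. This reproduces the stated 79% to 100% but has no bearing on the present point.

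Inputs: 30 intervention completers (the rule for ending enrolment, section 3.a.iii); about 15 controls, inferred from 2:1 allocation; and, as the upper case, the full allocation table of 67 and 33 (section 3.a.viii). The shift b, in SD units, is assumed.

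- Standard error of a standardised mean difference: SE = √(1/n₁ + 1/n₂).
- 30 v 15: SE = √(1/30 + 1/15) = 0.316; half-width 1.96 × 0.316 = 0.62 SD.
- 67 v 33: SE = √(1/67 + 1/33) = 0.213; half-width 1.96 × 0.213 = 0.42 SD.
- Coverage of a nominal 95% interval under bias b (normal approximation): Φ(1.96 − b/SE) − Φ(−1.96 − b/SE).

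| Assumed shift b (SD) | b ÷ 0.62 (30 v 15) | Coverage, 30 v 15 | Coverage, 67 v 33 |
|---|---|---|---|
| 0 | 0% | 95% | 95% |
| 0.1 | 16% | 93.8% | 92.4% |
| 0.2 | 32% | 90.3% | 84.4% |
| 0.3 | 48% | 84.2% | 70.8% |

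At the low end the effect on an exploratory interval is negligible. At the high end it is not, and it worsens as the sample grows, because the interval narrows around a shifted centre.

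**The case against.** The strongest reply is that the formal aim is not directional. Sections 2.a and 2.b frame the study as a test of whether Heartsight is feasible and acceptable, and Aim 1 covers recruitment, retention and engagement. A reminder confined to that would satisfy section 3.a.vi and prompt no particular answer. This stands as a possible reading. The goal sentence and the title also carry a direction, however, and the retention item does not say which is meant.

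A reader might infer that coordinators are instructed to state the expected benefit and then hand over the scale. The documents do not say this. That order is permitted but not written. Surveys can be completed asynchronously, and a reminder at pick-up would comply. The Visit 3 call also follows a linked script that is not part of the document and may already be neutral.

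A reader might also infer that biased mean differences would size the larger trial. Section 3.b.iii ties the sample-size calculation to the lower bounds of correlations. Read literally, that means the Exploratory Aim 1c associations and not clearly the 1a and 1b differences.

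Finally, participants learn the purpose at consent and can tell their arm, so only the added effect of repetition is at issue. That is correct, and it limits the size of the point. Retention is itself an Aim 1b outcome, with under 80% counted as not met, so weakening a retention measure is a real, if small, cost.

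**Conclusion.** The point holds as a minor one. The plan prescribes an aim reminder at the visits where unblinded self-report outcomes are collected, and the visible text neither makes it neutral nor defers it. This leaves an avoidable route for arm-differential reporting bias in Exploratory Aims 1a and 1b, probably in the favourable direction, though that direction is an expectation and not a demonstrated result.

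The size is unknown. The range of 0 to 0.3 SD is an assumption, and the true increment over consent may be near zero. The illustration also assumes 15 control completers, equal SDs and a normal approximation. Recruitment, retention and website-use outcomes are not biased by this route, and actigraphy sleep duration is largely unaffected. No sample-size figure in the plan changes.

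**What to change.** In section 3.a.vi, replace the aim reminder with a neutral one, worded identically in both arms: the remaining visit schedule, and that every participant's answers are equally useful. Add that at Visits 2 and 3 any discussion of the aim or of the expected benefit of Heartsight takes place only after the survey has been collected. For a paper survey at Visit 2, the pick-up contact already described in section 3.a.x serves. For REDCap this means after submission, and for a telephone survey after the last item. Check that the linked coordinator scripts agree.

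The cost is a sentence or two in the protocol, a small script edit and possibly a slightly weaker retention prompt. No staff, visits or data are added.

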#### **vii. Study Intervention**

The study intervention for RESURFACE is Heartsight, an online repository of bite-sized, lay-friendly informational articles developed by CA stakeholders for CA surrogates. Heartsight contains three packages of articles developed for specific timepoints in this study. The first two packages aim to reduce illness uncertainty among participants, whereas the third package aims to promote self-care and reduce caregiver burnout:

1. Understanding Cardiac Arrest (15 articles) - articles relevant to understanding CA and the ICU experience; delivered when participants are in the ICU
2. Preparing for Discharge (7 articles) - articles relevant to understanding post-hospitalization life, such as rehab options; delivered when participants are on the floor
3. Focusing on You (12 articles) - articles relevant to practicing self-care after returning home; delivered 3 months after hospital discharge

Study participants will receive unique login and password information for their Heartsight account, created for them by study staff, which will allow the study team to track intervention utilization through User Insights. User Insights enables the study team to track the articles read and time spent per article for each intervention arm participant.

Heartsight is accessible via any device with an internet connection.

#### **viii. Randomization**

[name] will be responsible for generating the randomization allocation table for the REDCap randomization module, which will assign participants to arms.

Method:

1. Before study launch, [name] will build a master randomization allocation table using Excel. This allocation table will yield arm assignments for 100 study participants (67 in the intervention arm, 33 in the control arm).
2. [name] will upload the allocation table to the REDCap randomization module.
3. Once the study launches, REDCap will switch to production mode, and the randomization module will be locked. Randomization assignments cannot be changed going forward.

4. When a new participant is recruited, study coordinators will click “Randomize” for a new record in REDCap. This will yield the arm assignment for the new participant, as determined by the pre-made allocation table.

